5.2 Enrollment and Follow up Procedures

Up to 72 evaluable HIV uninfected participants (54 non pregnant and 18 pregnant cisgender women) will be enrolled and followed up for 16 weeks: 8 weeks with DOT PrEP, and up to 8 weeks for post drug kinetics sampling – one visit in week 9 and an additional visit within weeks 10 to 16 (i.e. 2 visits in total). Enrollment must occur within 30-day screening window. An eligible participant who is unable to schedule a study entry visit within the 30-day screening window must be re-screened prior to entry into the study. All enrolments will be scheduled on specific days to avoid confusion in implementing the proposed dosing and sampling scheme. Study entry visit (enrollment) through week 8 visit will include an adverse effect questionnaire along with medical and medication review. Safety labs and vitals can be ordered as needed at any visit.

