5.2.2 Protocol pharmacology sampling visit schedule

On protocol-specified clinic visits (described below and Table 5), a blood sample will be collected from an arm vein for plasma/WB/RBC/DBS/PBMC isolation and safety laboratories. Hair will be cut from the scalp for comparison with other drug measures. Adverse events will be assessed. All protocol-specified clinic visits are detailed below. Each protocol-specified clinic visit will have a window of up to three days for sample collection (up to a week for hair).

Clinic visit 1: Study entry visit (must be within 30 days after screening visit)

- Medical, sexual, contraception, antenatal and vaccine history review
- Obtain study blood work: WB, DBS, PBMC, plasma, (pre-drug for endogenous molecules such as nucleosides)
- Urine β HCG
- Study urine: (baseline endogenous molecules such as nucleosides)
- STI tests (CT, GT, syphilis)
- hDNA
- Vaginal swab
- Dispense back up PrEP medication: subject home supply
- Dispense study dosing calendar
- DOT: Witness first PrEP dose

Clinic visit 2: Week 1 Dose 4 visit (for 2 doses per week group this will be 4 days since first dose:

- Study Bloodwork: WB, DBS, PBMC, plasma
- Study urine
- Finger stick for DBS
- Cervicovaginal biopsy: Random **subset (50%) of non-pregnant cohort only**
- Vaginal swab
- Medical, sexual, contraception, antenatal and vaccine history review
- AE assessment
- Concomitant Medication Review
- DOT

Clinic visit 3: Week 1 (Dose 7) visit:

- Study bloodwork: WB, DBS, PBMC, plasma
- Study urine
- Finger stick for DBS
- Vaginal biopsy: **Random subject (50%) of non-pregnant cohort only**
- Vaginal swab
- Blood work: hDNA for those who consent to drug transport gene testing.
- Medical, sexual, contraception, antenatal and vaccine history review
- AE assessment
- Concomitant Medication Review
- DOT

Clinic visit 4: Week 2 (Dose 14) visit:

- Study bloodwork: WB, DBS, PBMC, plasma
- Study urine
- Medical, sexual, contraception, antenatal and vaccine history review
- AE assessment
- Concomitant Medication Review
- DOT

Clinic visit 5: Week 3 (Dose 21) visit:

- Study bloodwork: WB, DBS, PBMC, plasma
- Study urine
- Medical, sexual, contraception, antenatal and vaccine history review
- AE assessment
- Concomitant Medication Review
- DOT

Clinic visit 6: Week 4 (Dose 28) visit:

- HIV rapid test
- Urine β HCG
- Study bloodwork: WB, DBS, PBMC, plasma
- Study urine
- Vaginal biopsy: **Non-pregnant cohort only**
- Vaginal swab
- Hair collection

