- Urine pregnancy test
- Medical, sexual, contraception, antenatal and vaccine history review
- AE assessment
- Concomitant Medication Review
- DOT
- Finger stick for DBS

Clinic visit 7: Week 5 (Dose 35) visit:

- Study bloodwork: WB, DBS, PBMC, plasma
- Study urine
- Medical, sexual, contraception, antenatal and vaccine history review

- AE assessment
- Concomitant Medication Review
- DOT

Clinic visit 8: Week 6 (Dose 42) visit:

- Study bloodwork: WB, DBS, PBMC, plasma
- Medical, sexual, contraception, antenatal and vaccine history review
- AE assessment
- Concomitant Medication Review
- DOT
- Study urine

Clinic visit 9: Week 7 (Dose 49) visit:

- Study bloodwork: WB, DBS, PBMC, plasma
- Study urine
- Medical, sexual, contraception, antenatal and vaccine history review
- AE assessment
- Concomitant Medication Review
- DOT

Clinic visit 10: Week 8 (Dose 56) visit:

- HIV rapid test
- Urine β HCG
- Study bloodwork: WB, DBS, PBMC, plasma
- Finger stick for DBS
- Study urine
- Vaginal biopsy: **Non-pregnant cohort only**
- Vaginal swab
- Hair collection
- Safety Labs: Creatinine
- Medical, sexual, contraception, antenatal and vaccine history review
- AE assessment
- Concomitant Medication Review
- DOT

Post DOT PrEP visits (Week 9): One visit (Clinic visit #11) within week 9, at least 48 hours after the last DOT PrEP dose.

- Study bloodwork: plasma, WB, DBS, PBMC
- Study urine

Post DOT PrEP visits (Week 10-16): One visit (Clinic visit #12) at least 7 days after week 9 visit (i.e., the visit can occur any time between 2-8 weeks after the last DOT F/TAF PrEP which is about week 10 and week 16 since enrollment)

- Study bloodwork: plasma, WB, DBS, PBMC
- Study urine
- Hair collection

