6.10 Reporting Requirements for this Study

The study agents for the purposes of SAE/EAE reporting are part of a fixed dose combination tablet of FTC/TDF (also outlined in Section 4).

For each study participant, the SAE/EAE reporting period begins at Enrollment (Day 0) and ends when the participant's follow-up in the study ends (at the Week 9 Visit). All reportable SAEs occurring during the study reporting period will be reported to the principal investigator and for EAEs to the DAIDS RSC Safety Office in an expedited manner, within three reporting days of site awareness of the events (see definition in Appendix D of the DAIDS EAE Manual). After the study has ended, sites must report Suspected Unexpected Serious Adverse Reaction (SUSARs) as defined in Version 2.0 of the DAIDS EAE Manual if the study site becomes aware of the event on a passive basis, i.e., from publicly available information. Site staff will also report information regarding SAEs to their IRB or other local regulatory agencies in accordance with all applicable regulations and local IRB requirements.

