8.4 Potential Risks to Human Subjects

Safety assessment will be measured in all participants: serious adverse events (SAEs), related Grade 3 and 4 AEs and discontinuations, and a side effects. The medical risks of blood collection and vaginal tissue collection are small, with some anticipated mild discomfort from vaginal speculum insertion, and venipuncture. Participants may become embarrassed, worried, or anxious while undergoing pelvic exams for collection of samples.

Risks related to non-daily PrEP dosing

Participants will be randomized to one of 3 directly observed dosing patterns: 2, 4 or 7 TDF/FTC doses per week. Only daily PrEP is recommended by WHO and the Kenya national guidelines for protection from vaginal HIV exposure and we have carefully considered the risks associated with non-daily in planning this proposal. We have carefully considered the risk associated with using non-daily dosing for PrEP (i.e., 2 or 4 doses per week) in non-pregnant cisgender women and the potential for risk of HIV infection for those non-daily dosing. The non-daily dosing is needed to help investigate and demonstrate dose proportionality of TFV and TDF-DP concentrations. The adherence-concentration thresholds derived from this dosing frequency will be important to estimate efficacy levels derived from varying adherence patterns, including suboptimal dosing. As detailed in [eligibility section](#), only cisgender women at low risk of HIV based on Kenya guidelines will be enrolled and cisgender women will receive full package of HIV prevention, including risk reduction counseling, condoms and STI treatment at each visit. We will also perform monthly HIV testing. We will use Kenya national guidelines to guide identification of cisgender women at elevated risk of HIV to guide recruitment into this study. Each visit will include risk-reduction counseling for all cisgender women. All participants in this study will have HIV test at baseline and then every 4 weeks and PrEP will be immediately discontinued in case of seroconversion.

Risks related to TDF/FTC PrEP

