8.5 Approaches to Minimize Risks

Protection of risks related to non-daily PrEP dosing

We have carefully considered the risk associated with using non-daily dosing for PrEP (i.e., 2 or 4 doses per week) in non-pregnant cisgender women and the potential for behavior disinhibition as a result of PrEP is an important outcome. We will make all effort to enroll only healthy cisgender women volunteers deemed at low risk for HIV. We will use Kenya national guidelines as well as published HIV risk score (Voice risk) to guide identify cisgender women who may be at elevated risk of HIV to guide recruitment into this study—those found to at elevated risk for HIV will be immediately linked for PrEP and other prevention services here at the Thika site or at the participants' clinic of choice. Each visit will include risk-reduction counseling for all cisgender women. All participants in this study will have HIV test at baseline and then every 4 weeks and PrEP will be immediately discontinued in case of HIV seroconversion. Non-pregnant cisgender women identified to be at elevated risk of acquiring HIV through screening will be immediately linked for PrEP at study clinic site itself or at participant's clinic of choice.

Protection against risks related to TDF/FTC PrEP

All participants will have HIV testing, creatinine testing, hepatitis B, and urine pregnancy testing at baseline. Only cisgender women with creatinine clearance >60 mL/min and uninfected with hepatitis B will be enrolled. We are testing volunteers for HBV-infection to protect subjects from HBV-associated hepatitis flares when the drugs are withdrawn. Breastfeeding will not be allowed to prevent risks to nursing infants. We are excluding subjects who have serious underlying illnesses such as cancer and heart disease. All clients will be counseled about potential side effects at enrollment and each follow up visit and they will be reminded that the side effects are self-limiting within 1-2 weeks. Subjects will be followed with clinical laboratories at entry and 8 weeks (serum creatinine, complete hematology, monthly pregnancy urine test) and more frequently with interviews to assess tolerability and safety over the course of the study, including during directly observed dosing. Participants will be tested for HIV infection at any point during the study as needed, and prior to and at the final visits of the dosing periods.

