9 LABORATORY SPECIMENS AND BIOHAZARD CONTAINMENT

9.1 Laboratory evaluations and specimen collections

The following safety and monitoring laboratories will be collected at regular intervals during the study as described above: complete hematology panels, pregnancy tests (urine), and HIV (rapid or regular), serum creatinine, (estimated creatinine clearance), and HBV surface Ag test. The HIV and HBV tests will be used to screen HIV-negative volunteers for inclusion in the study. The tests are provided according to established laboratory procedures at site. These clinical laboratories/sites conform to CAP and/or CLIA-regulations, and the results will be posted to the medical record as positive or negative.

All pharmacological samples will be collected, processed, and stored according to standard operating procedures developed by the Colorado Antiviral Pharmacology Laboratory. On each pharmacological sample visit day, samples will be collected without regard to the dosing time within each day (i.e., sampling at convenience times rather than troughs). The only exception will be at the entry visit to be obtained at pre-dose. We will take a comprehensive approach to establish benchmark adherence-concentration thresholds for cisgender women and pregnant cisgender women using daily DOT TDF/FTC

PrEP by collecting samples for pharmacological measurements in multiple biologic matrices: plasma, whole blood, DBS, PBMCs, and vaginal tissue (non-pregnant cisgender women only) and archiving urine and hair samples. All cisgender women (non-pregnant and pregnant) will contribute to this comprehensive assessment during the up to 16 weeks of follow up (8 weeks of DOT PrEP and up to 8 weeks post DOT PrEP for post drug kinetics). Within each group, we will collect pharmacologic samples (plasma, whole blood, DBS, PBMCs) to measure the respective concentrations of TDF/FTC moieties at day 4 and weekly up to 8 weeks with daily DOT PrEP dosing and at week 9 and weeks 10-16 post DOT PrEP period, and in nonpregnant cisgender women, vaginal tissue at day 4, week 1, 2, 4, and 8.

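### Section 6.10 closes SAE/EAE reporting at week 9 although follow-up runs to weeks 10–16 and past delivery, and no adverse-event question is scheduled after week 8

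*Combined protocol and SAP*

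**What the plan says.** **Reporting period.** Section 6.10 starts the SAE/EAE reporting period at enrollment and closes it when "follow-up in the study ends (at the Week 9 Visit". The rule is the end of follow-up; the date given for it is week 9.

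**Length of follow-up.** Section 5.2 plans 16 weeks per participant, with two visits after dosing stops. Section 5.2.2 describes visit 11 as "One visit (Clinic visit #11) within week 9, at least 48 hours after the last DOT PrEP dose". Of visit 12 it says "the visit can occur any time between 2-8 weeks after the last DOT F/TAF PrEP", which it equates to about weeks 10 to 16 (the product named there is a slip; the study drug is TDF/FTC). Section 9.1 has samples collected "during the up to 16 weeks of follow up (8 weeks of DOT PrEP and up to 8 weeks post DOT PrEP". Section 5.2.1 and Table 5 agree. For the pregnant cohort, section 5.4 adds maternal and infant visits at 1, 6 and 12 months after delivery, or until the study ends if that is sooner, and records birth defects among the outcomes. Section 6.6 counts a birth defect as an SAE.

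**Adverse-event questions.** Section 5.2 states "Study entry visit (enrollment) through week 8 visit will include an adverse effect questionnaire along with medical and medication review". Table 5 and the visit lists in section 5.2.2 agree: the last adverse-event assessment is at visit 10 (week 8). Visit 11 lists study blood and urine only; visit 12 adds hair.

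**The concern.** The sentence in section 6.10 contradicts itself when set beside the schedule, because follow-up does not end at week 9. A site working from the date would treat an SAE between visits 11 and 12 as outside the reporting period while the woman is still in the study. It would do the same for a birth defect found at delivery, although the protocol sets up visits to look for exactly that.

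The second matter is a gap in the schedule, not a contradiction. Section 8.4 calls the vaginal biopsy invasive and names discomfort, pain and possible bleeding. Every non-pregnant woman is due her last biopsy at the visit where adverse-event questioning also ends. Delayed complications of that biopsy, and drug events that appear after dosing, are recorded only if the woman volunteers them or staff notice them.

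**Working it through.** The plan gives no figure to reproduce. The check is a comparison of sections plus calendar arithmetic.

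**1. Reporting gap up to visit 12.** Section 6.10 closes at week 9. Sections 5.2 and 5.2.2 and Table 5 put visit 12 in weeks 10–16.

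- Shortest gap: 10 − 9 = 1 week. Section 5.2.2 also requires at least 7 days between the two visits.
- Longest gap: 16 − 9 = 7 weeks.
- In person-time for 54 non-pregnant women: 54 × 1/52 = 1.04 to 54 × 7/52 = 7.27 person-years.

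**2. Reporting gap, pregnant cohort.** Gestation at enrollment is 13–26 weeks (section 2.5.2). At the week-9 cut-off it is 13 + 9 = 22 to 26 + 9 = 35 weeks. Section 3.1 applies the gestation limit at screening, and entry may follow by up to 30 days (30/7 = 4.3 weeks), so the extreme upper end is 35 + 4.3 = 39.3 weeks. Even on that reading, only women near the top of the range with a long screening interval could deliver before the cut-off. Section 3.2 already excludes known or suspected major anomalies, and the Birth Visit takes place at month 1 after delivery. Most newly found birth defects would therefore come to light after the stated period.

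**3. Adverse-event gap.** The last scheduled assessment is at week 8. Visit 12 comes 10 − 8 = 2 to 16 − 8 = 8 weeks later, and visit 11 about one week later. Neither visit lists an adverse-event question.

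**4. What each biopsy gets** (Table 5 with footnote f, and the visit lists):

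| Biopsy | Women | Assessment at the same visit | Next scheduled assessment |
|---|---|---|---|
| Day 4 | random half | yes | day 7, nominally 3 days later |
| Day 7 | other half | yes | week 2, nominally 7 days later |
| Week 4 | all | yes | week 5, nominally 7 days later |
| Week 8 | all | yes | none |

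Each woman has three biopsies: one in week 1, one at week 4 and one at week 8. With 54 women that is 54 × 3 = 162, of which 54 (54/162 = 33%) are at week 8. Section 3.1 asks for at least 7 days' sexual abstinence after each biopsy. For the last one, that period ends at about visit 11, when the woman is in front of study staff.

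**The case against.** **On the date.** It can be said that this is an editorial slip with limited effect. The rule itself is tied to follow-up, and neither the recording of adverse events in section 6.3 nor the SAE reporting in section 6.6 carries a week-9 limit. There is a 24-hour telephone line, section 5.4 has pregnant women followed closely for adverse events, and section 7.6 has pregnancy outcomes reviewed. All of this stands. It lowers the chance that an event is lost, and it does not support a claim that SAEs will go unreported. None of it corrects the one sentence that defines the reporting period.

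**On the week-8 biopsy.** A reader might infer that it gets no adverse-event assessment at all. That is wrong: visit 10 lists both the biopsy and the assessment. Only later complications go unasked.

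**On conflict with the general text.** A reader might set the introduction to section 5.2.2, "Adverse events will be assessed. All protocol-specified clinic visits are detailed below", against Table 5. That paragraph defers to the visit details and Table 5. It lists hair and safety laboratories in the same breath, and these are plainly not due at every visit. It is a menu of procedures and does not contradict the schedule.

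**On HIV and pregnancy tests.** A reader might also take "All participants in this study will have HIV test at baseline and then every 4 weeks" as a promise that runs past week 8. In sections 8.4 and 8.5 that statement continues with stopping PrEP on seroconversion, and section 4.8 gives prompt cessation of study drug as the purpose. Section 8.5 also places testing "prior to and at the final visits of the dosing periods". Baseline, week 4 and week 8 is four-weekly testing over the dosing period, as Table 5 has it. The pregnancy-test version rests on one mention of monthly testing in section 8.5, inside a list tied to entry and week 8. The documents do not support a conflict on either test, and I propose no added tests.

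**Conclusion.** Two modest points hold.

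- **The end date in section 6.10 is wrong as written.** It leaves 1–7 weeks of scheduled follow-up per non-pregnant woman, and most of the period in which birth defects would be found, outside the stated SAE/EAE window. This follows from the protocol's own visit timing and needs no assumed event rate. The person-time figure assumes that all 54 non-pregnant women are enrolled and reach visit 12.
- **Visits 11 and 12 lack an adverse-event question.** Delayed complications of one third of the biopsies, and late drug events, depend on spontaneous report. The documents give no complication rate, so I put no number on missed events.

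The primary pharmacokinetic analysis is unaffected. The point is worth fixing because the date is plainly inconsistent and the added safety information costs very little.

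**What to change.** 1. **Section 6.10.** Replace the parenthesis that names the Week 9 visit with the participant's last visit after dosing (visit 12). For the pregnant cohort, state a separate end point that covers pregnancy outcome and the infant observation visits in section 5.4. This is needed because section 5.4 offers visits 11 and 12 only to pregnant women who choose not to continue PrEP.
2. **Table 5 and section 5.2.2.** Add adverse-event assessment and concomitant-medication review at visits 11 and 12. Change the week-8 limit in the section 5.2 sentence to match.

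**Cost.** At most 54 × 2 = 108 short questionnaires in the non-pregnant cohort. If every pregnant woman stopped PrEP and attended both visits, there would be up to 18 × 2 = 36 more. All are at visits already planned; no visit moves and no sample is lost. The SAE reporting period becomes longer, by 1–7 weeks for non-pregnant women and by more for the pregnant cohort, with the reporting work that this brings.

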5.2.1 Dosing schedule and assessment of compliance

The design of the study is guided by the ~17 day half-life of TFV-DP in DBS, including 8 weeks of dosing to achieve approximately 90% of steady-state, weekly sampling at convenience times (i.e., rather than troughs), and three dosing groups (2, 4, and 7 doses per week) to demonstrate dose-proportionality. All cisgender women will be followed for 8 weeks with DOT PrEP to establish steady state in DBS and WB, and up to 8 weeks for two post-DOT PrEP sampling visits. We have chosen a dosing frequency scheme for non-daily doses to directly replicate the STRAND DOT study schedule based on the ~17 day half-life of TFV-DP in DBS: The 2 doses per week will be taken on Monday and Tuesday, and the 4 doses per week on Monday, Tuesday, Thursday, and Friday. This schedule will permit simultaneous evaluation of concentrations derived from intermittent and day-by-day dosing. The operationalization of specific days for dose taking can be adjusted prior to study start while maintaining the randomized adherence patterns (frequency of dosing taking) to permit efficient study operations and to minimize the burden on study participants. This is possible due to TFV-DP long half-life and planned sampling at steady state. Therefore, any chosen days would still be appropriate.

All doses will be witnessed, as described above, in person by a study personnel in private room at the Thika clinic or other predetermined location to maximize convenience for the participant. On dosing visits, the participant will take the dose by mouth and study personnel will ensure the tablet is swallowed by

asking the participant to show that their mouth is empty. Flexible clinic scheduling will be available to promote high rates of follow-up and compliance and minimize participant's burden. Where dosing cannot be witnessed in person, dosing will be witnessed by video communication via WhatsApp, Zoom, FaceTime, Skype, or other video-streaming device that is agreed upon by the participant and study personnel will be used. Only cisgender women with an active smart phone will be enrolled in this pharmacological study to permit offsite observation of dose taking for the required DOT PrEP. Participants will be supported with commensurate data/internet bundles. A one-month supply of back-up medication will be provided to participants at study enrollment to be used if participant is unable to complete visit at the clinic. All these doses taken offsite will still be directly observed by study staff by live video streaming and participants will be asked to open their mouth afterwards to confirm swallowing. Dosing may occur at variable times within the assigned dosing day. All doses will be taken without regard to food, but meal information will be collected with each dosing event.

Study personnel will use a dosing log to document directly observed doses. Participants will be given a detailed calendar that shows scheduled dosing days. This schedule will also be reinforced when study personnel interact with participants.

